4. INTERIM ANALYSIS AND DATA MONITORING COMMITTEE

One interim analysis was planned and conducted after 50 deaths. The primary purpose of the interim analysis was to evaluate safety, efficacy, and sample size assumptions. This analysis included an assessment of the primary outcome (RSFDs) and mortality.

The interim analysis was conducted by the unblinded statistical team and reviewed by the independent Data and Safety Monitoring Board (DSMB). Based on pre-specified stopping boundaries and overall risk-benefit assessment, the DSMB recommended continuation of the trial without modification. No additional interim analyses were performed.

DSMB meetings were conducted on the following dates:

DSMB	1/10/2022
DSMB	7/8/2022
DSMB	8/30/2022
DSMB	1/26/2023
DSMB	8/11/2023
DSMB	2/8/2024
Interim Analysis	7/8/2024
DSMB	10/1/2024

The trial was paused for enrollment on July 22, 2022, to allow the DSMB time to review the updated dataset, and enrollment resumed on September 9, 2022. A closed enrollment decision was later made by NHLBI due to safety and futility concerns following the last DSMB meeting on October 1, 2024.

5. GENERAL ANALYSIS METHODS

Primary Endpoint

To evaluate the primary hypothesis—that the mean difference in respiratory support-free days (RSFDs) between the two treatment groups is significantly different from zero—we will use a two-sample parametric t-test as the primary statistical test. This test is known for its robustness to violations of normality when the sample size is sufficiently large ($n > 25$), as is the case in this trial.

To support and validate the primary analysis, we will also conduct a two-sample permutation t-test. This nonparametric test requires only the assumption of exchangeability, which is satisfied in the context of a randomized controlled trial. The permutation test provides a distribution-free confirmatory approach, reinforcing the robustness of our findings.

In addition, we will apply the semiparametric efficient and robust estimation procedure proposed by Davidian et al. [7,8] to estimate the mean treatment difference in RSFDs along with a 95% confidence interval. This method adjusts for baseline covariates predictive of the outcome, thereby improving both statistical efficiency and precision relative to unadjusted comparisons or traditional ANCOVA. This analysis also accommodates missingness in the primary endpoint (excluding death) by explicitly modeling the missing data mechanism, as described in Protocol Section 6.4.1.

In addition to the primary analysis using the main intent-to-treat (ITT) population, we will conduct sensitivity analyses using the classical ITT (cITT) and two modified ITT (mITT) analysis sets to assess the robustness of results.

Secondary endpoints

For quantitative secondary endpoints, including the key secondary endpoint of ventilator-free days (VFDs), we will apply the same analytic approach as described for the primary endpoint (RSFDs), including both unadjusted and adjusted methods using the semiparametric efficient and robust procedure proposed by Davidian et al. [7, 8]. In addition, analyses will be conducted on total RSFDs without the last-off approach, to assess consistency across definitions.

For time-to-event secondary endpoints, such as CMV reactivation at pre-specified thresholds, the Kaplan-Meier method will be used to estimate the probability of not experiencing the event by Day 28 for each treatment group. A 95% confidence interval for the between-group difference in event rates will be constructed using the Greenwood variance estimator. Between-group comparisons will be performed using a Z-test based on the Kaplan-Meier survival function estimates. Where applicable, Bonferroni correction will be used to adjust for multiple comparisons across secondary endpoints.

[figure not shown]
Additionally, multivariable models will be constructed for the primary endpoint (RSFDs) and other secondary outcomes to adjust for baseline characteristics and known risk factors for CMV reactivation. These models may include generalized linear models (GLMs) or the semiparametric method of Davidian et al., depending on the outcome type and distributional assumptions. The covariates considered will correspond to those outlined under exploratory objectives in Protocol Section 5.3.

As a secondary objective, we will assess whether the treatment effect varies by treatment period (i.e., during vs. post-drug exposure). Specifically, for mortality, we will test for treatment-by-period interaction to explore whether the timing of Ganciclovir exposure modifies the risk of death. If interaction is present, stratified or time-varying effect models will be considered in post hoc exploratory analyses.

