2.3 Randomization

Patients who met all inclusion and exclusion criteria were randomized to receive standard ICU care (including lung-protective ventilation and weaning protocols, if mechanically ventilated) plus either the intervention or placebo. Randomization was stratified by site and implemented using block randomization lists created by SCHARP. Assignment was conducted through the Medidata RTSM system.

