8. PRIMARY ENDPOINT ANALYSES

The primary endpoint, respiratory-support-free days (RSFDs), is defined as 28 days minus the number of days a participant received respiratory support (including invasive mechanical ventilation, non-invasive ventilation with CPAP or bi-level CPAP and PEEP ≥ 5 cmH₂O, or high-flow nasal cannula oxygen with a flow rate ≥ 30 L/min) through Day 28 following randomization.

- Participants who do not survive through Day 28 will be assigned zero RSFDs.
- Participants who remain on respiratory support on Day 27 will be assigned zero RSFDs.
- Participants transferred to long-term acute care hospitals (LTACHs) will be assigned zero RSFDs.
- Participants who withdrew consent, refused further participation by themselves or a legally authorized representative (LAR), and for whom no further data were collected, or who withdrew due to study closure within the first 28 days will be considered missing for the RSFD endpoint.

RSFDs will be summarized descriptively using the mean, standard deviation, median, and range by treatment group. To formally test the primary hypothesis that the mean difference in RSFDs between treatment arms differs from zero, a two-sample parametric t-test will be used. This test is appropriate even if the normality assumption is mildly violated, given its robustness for moderate sample sizes ($n > 25$). As a confirmatory approach, a two-sample permutation t-test will also be performed. This nonparametric test does not require distributional assumptions and is valid under the weaker condition of exchangeability, which is satisfied in the randomized trial setting.

To further improve statistical efficiency and precision, the semiparametric efficient and robust method of Davidian et al. [7, 8] will be employed to estimate the mean difference between arms, along with its 95% confidence interval. This method adjusts for baseline characteristics predictive of the primary outcome and is more powerful than a conventional ANCOVA or t-test when baseline adjustment is warranted. If data on

the primary endpoint are missing for reasons other than death, the analysis will appropriately account for the missing data mechanism, as described in Protocol Section 6.4.1.

In addition to the ITT analysis, the primary endpoint will also be analyzed in a classical intent-to-treat (cITT) and two modified intent-to-treat (mITT) populations.

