4 RATIONALE

The study is a phase 3 randomized, double-blind, placebo-controlled multicenter (see Appendix H for a list of the 19 initial clinical sites) clinical trial with respiratory-support-free days (RSFD) as the primary outcome measure. The rationale for key aspects of the study design are summarized in Table 4-1 and described below.

Table 4-1. Rationale for Key Aspects of the Study Design.

Study Population		
Sepsis, Acute Respiratory Failure, and Respiratory Support are defined as in Section 4.1.1 below.		
Prophylaxis vs. Treatment		
	PROS	CONS
Prophylaxis	
 Conceptually more attractive; prevents all CMV reactivation at any site (including lung) before CMV-associated effects begin Standard of care for other populations where CMV is a clinical problem (transplantation) Best experimental/clinical data for preventing CMV indirect effects Logistically easier (would also be easier to implement clinically) 	
 Effect “diluted” by high proportion of non-reactivators Relative “over-treatment” with risk for drug toxicity
Treatment (Preemptive Therapy)	
 More targeted approach (“treating a known/diagnosed infection” vs. preventing a theoretical possibility) Minimizes drug exposure and toxicity by targeting only infected patients 	
 Logistically complicated Likely too late to see any benefit of intervention (CMV-mediated effect cascade already initiated) [10] Less effective in animal models Plasma CMV PCR is an insensitive marker of CMV reactivation (preferentially local reactivation in lung)
Choice of Drug		
Ganciclovir	
 FDA-approved for prophylaxis and treatment of CMV infection and disease Favorable safety profile in ICU patients Extensive experience in patients with reduced renal function Insufficient data for alternative drugs (letermovir, maribavir) Broad-spectrum antiviral activity (including HHV-6 [71]) 	
Study drug duration		

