6.3 Randomization scheme

The randomization sequence will be uploaded by SCHARP into the Medidata's Randomization and Trial Supply Management (RTSM) system and provided to each site through Medidata. The randomization will be block-randomized by site. At each institution, the pharmacist with primary responsibility for drug dispensing is charged with maintaining the security of the randomization list. A research pharmacy designee may be provided access to the randomization assignment from Medidata RAVE.

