9.5 Randomization procedure

Randomization will occur after assessment of positive CMV serostatus as detailed in **Section 9.3.1**, and negative pregnancy test. Randomization and first dose of study drug should occur as close to each other as possible. Randomization and first dose of drug **must** occur within 120 hours of hospital admission **and** on the same calendar day. Patients who are randomized but in whom the need for respiratory support ends, who die, are outside of the 120 hour window, or have consent withdrawn before receiving first dose of study drug should not receive their first dose of drug and are withdrawn from the study (see Section 7.5).

The randomization sequence will be uploaded by SCHARP into the MediData's Randomization and Trial Supply Management (RTSM) system and provided to each site through MediData. This

system automatically notifies the site pharmacist of the treatment assignment. The randomization will be block-randomized by site. At each institution, the pharmacist with primary responsibility for drug dispensing is charged with maintaining the security of the randomization list. Patients will be stratified at the time of randomization according to treatment center.

When the patient is randomized, the following information is required by NIH reporting guidelines: date of birth, race/ethnicity, and gender. For the purpose of this study, each patient will be assigned a study number, which will be used for all communications with outside institutions to assure confidentiality.

A CLIA-certified standard serologic assay will be used to confirm CMV positivity, but patients with a positive rapid test result may be randomized prior to the return of the CLIA test results (see **Section 9.3.1**).

Randomization will continue until the target accrual number for participants in the primary analysis are met. The primary analysis population will be all patients randomized who receive at least one dose of the assigned study product.

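### Randomization was stratified by site, but the RSFD t-test and permutation test do not take site into account and the semiparametric estimate does not name it; the t-test stays valid but is slightly conservative

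*SAP*

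**What the plan says.** On the design, SAP Section 2.3 states: "Randomization was stratified by site and implemented using block randomization lists created by SCHARP". Protocol Section 6.3 agrees ("The randomization will be block-randomized by site"), and so does Protocol Section 9.5 ("Patients will be stratified at the time of randomization according to treatment center"). Site is the only stratum named. Protocol Section 4 gives its initial number: "see Appendix H for a list of the 19 initial clinical sites".

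On the analysis of RSFDs, SAP Sections 5 and 8 and Protocol Section 6.2.1 plan three steps:

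- **Primary test.** "we will use a two-sample parametric t-test as the primary statistical test". No site term is mentioned.
- **Confirmatory test.** SAP Section 8 adds that "a two-sample permutation t-test will also be performed". SAP Section 5 justifies it so: "This nonparametric test requires only the assumption of exchangeability, which is satisfied in the context of a randomized controlled trial". Neither section says that labels are permuted within site.
- **Semiparametric estimate.** "This method adjusts for baseline covariates predictive of the outcome". No list is given there. Protocol Section 6.2.1 names gender and race/ethnicity. The exploratory factors in Protocol Section 5.3, to which the adjusted models refer, are all patient-level.

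For RSFDs, site is named only in SAP Section 11, as a factor for exploratory subgroup analyses that are placed outside the final study report.

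**The concern.** Blocking within site balances the arms in every site, so differences between sites largely cancel out of the treatment comparison. A plain two-sample t-test still counts those differences as noise. Its standard error is then somewhat too large, its interval somewhat too wide, and its true type I error below the nominal 5%.

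The permutation test has the same feature if labels are shuffled across the whole trial, because that reference distribution includes imbalances between sites that the design does not allow. The exchangeability guaranteed by the design is within blocks within site. The test is offered to validate the primary analysis, yet in this form it would agree with the t-test without revealing the conservatism.

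The stake is modest precision. It has some practical weight because enrollment was closed early over safety and futility (SAP Section 4), so interval width affects how far benefit or harm can be ruled out.

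**Working it through.** **Inputs from the documents.** Difference 2.74 days, SD 9.4 days, two-sided 5%, 85% power, 213 per arm (SAP Section 2.5; Protocol Section 6.1.1); 19 initial sites (Protocol Section 4). **Assumed.** Site ICC, block size and site sizes are not given. ICCs of 0.02, 0.05 and 0.10 are used, and results are listed in that order.

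**1. The plan's own figure.** The t-based sample size for these inputs is 212.3, rounded up to 213 per arm or 426 in all. The plan's figure reproduces. Power at 213 per arm is 85.1% (t) or 85.3% (normal approximation).

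**2. Standard errors.** The t-test uses SE = 9.4 × √(2/213) = 0.911 days. With balance within sites, the true SE is 0.911 × √(1 − ICC) = 0.902, 0.888, 0.864 days.

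**3. Actual type I error of the t-test.** 2 × [1 − Φ(1.96/√(1 − ICC))] = 4.8, 4.4, 3.9%.

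**4. Power at 213 per arm.**

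- t-test, Φ[(2.74/0.911 − 1.96)/√(1 − ICC)]: 85.5, 85.9, 86.5%.
- With a site term, Φ[2.74/(0.911 × √(1 − ICC)) − 1.96]: 86.0, 87.0, 88.7%.
- Gain from unrounded values: 0.4, 1.1, 2.2 points. At 250 per arm it is 0.3, 0.8, 1.5. At 175 per arm it is 0.6, 1.5, 2.9; this size is illustrative, since the final number enrolled is not given.

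**5. Half-width of the 95% interval at 213 per arm.** 1.96 × 0.911 = 1.79 days for the t-test; 1.77, 1.74, 1.69 days with a site term.

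**6. Simulation with realistic outcomes.** Outcomes were shaped on Protocol Table 6-1, with 19 sites of 5 to 59 patients, N = 426, blocks of 4, 999 permutations and 10,000 runs per scenario. The linear model has arm and site, with sites under 8 patients pooled.

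| | ICC 0 | 0.02 | 0.05 | 0.10 |
|---|---|---|---|---|
| Null, t-test | 5.0% | 4.5% | 4.2% | 4.0% |
| Null, unrestricted permutation | 5.1% | 4.5% | 4.2% | 4.0% |
| Null, within-site permutation | 5.0% | 4.7% | 4.8% | 5.1% |
| Null, linear model with site | 5.0% | 4.7% | 4.8% | 4.9% |
| Power, t-test | 85.3% | 85.4% | 85.9% | 86.9% |
| Power, unrestricted permutation | 85.0% | 85.1% | 85.7% | 86.8% |
| Power, within-site permutation | 85.2% | 85.6% | 86.7% | 88.6% |
| Power, linear model with site | 85.2% | 85.7% | 86.6% | 88.7% |

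Monte Carlo error is about 0.2 points under the null and 0.3 to 0.4 for power. At ICC 0.02 the differences are within or close to that error. Blocks of 2, 6 or 8 give the same picture at ICC 0.05: 4.3% for the t-test and 4.8 to 4.9% for within-site permutation.

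**7. How site enters the semiparametric estimate.** Simulations at N = 350 and 426 (3,000 runs; error √(0.05 × 0.95/3000) ≈ 0.4 points) gave these null rejection rates:

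- arm-specific site means, no small-sample variance correction: about 5.5 to 6.4%;
- common site effect, degrees-of-freedom correction: 5.0 to 5.5%;
- linear model with site: 4.9 to 5.4%.

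A larger run of the first version (20,000 null runs) gave 5.5, 5.5, 5.4% at N = 426 and 5.8, 5.9, 5.3% at N = 350. The linear model on the same data gave 4.9, 4.9, 4.8% and 5.0, 5.1, 4.6%.

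**The case against.** The case for leaving the plan alone is substantial.

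- **There is no shortfall.** Power of the t-test is at or above 85% at every assumed ICC, and its type I error does not exceed 5%. This stands. A reader might infer that ignoring the stratum inflates false positives, invalidates the primary test or makes the sample size wrong. The documents and the arithmetic support none of these; the error is on the conservative side and 213 per arm reproduces.
- **The primary result would not change.** This also stands, since the t-test is kept. Only the supporting analyses gain.
- **The size is assumed.** No document supports any particular ICC, and the clearer effects need 0.10. This stands too, but if sites do not differ, adjustment costs almost nothing (the ICC 0 column).
- **Site is not excluded.** A reader might infer that no planned RSFD analysis uses site. That goes too far. A site effect would fit the semiparametric method's general description of predictive baseline covariates, and site is an exploratory subgroup factor. The accurate statement is that nothing commits the analyst to include it.
- **The change comes late.** The unblinded team assessed RSFDs at the interim analysis, and permuting within site raises the confirmatory test's rejection rate (at ICC 0.05, from 4.2 to 4.8% under the null). This calls for care. The restriction follows from the randomization and not from outcome data, and the governing test is untouched. The two tests may still disagree near 0.05, so a rule is needed.
- **Naming site is not automatically harmless.** Step 7 shows this to be right for arm-specific site means without a variance correction.

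**Conclusion.** The point holds as a modest, inexpensive improvement. The analyses do not follow the one stratum used in randomization. The t-test lacks it, the permutation test is not restricted to it, and the semiparametric estimate leaves it unspecified. The consequence is slight conservatism: about 0.2 to 1.1 points of type I error left unused, and up to about 2.2 points of power forgone at 213 per arm, for assumed ICCs between 0.02 and 0.10. With no differences between sites, nothing is lost. These sizes rest on assumed ICCs and on arms balanced within sites; the simulations also assume site sizes and block sizes. The primary test needs no change.

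**What to change.** 1. Keep the prespecified t-test as the primary test, and state in SAP Sections 5 and 8 that it governs the conclusion if a supporting analysis falls on the other side of 0.05.
2. In the same sections, state that permutations are done within site.
3. Add a linear model with arm and site as a supporting RSFD analysis. Pool very small sites by a rule fixed in advance on patient counts only, for example fewer than 8 patients.
4. If site is also named in the semiparametric estimate, enter it as a common effect and not arm by arm, with a small-sample or degrees-of-freedom correction to the variance.
5. Record these changes in SAP Section 12 before the final analysis.

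The cost is wording, one extra model and no new data. The linear model uses about 19 − 1 = 18 degrees of freedom for the 19 initial sites, fewer after pooling and more if sites were added. The supporting analyses may differ from the t-test near 0.05, which item 1 settles.

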2.1 General Design Considerations

The following is a summary of the protocol.

Short Title: A Phase 3 Study of Ganciclovir Use in Patients with Acute Respiratory Failure and Sepsis

Funder: NHLBI

Protocol Team: [name], PhD
 [name]
 [name]
 [name], MSc

Sample Size: Approximately 500 participants

Study Population: Immunocompetent, CMV seropositive adults hospitalized with sepsis and acute respiratory failure requiring respiratory support

Study Sites: Sites selected by the GRAIL Executive Committee

Study Hypotheses: We hypothesize that IV ganciclovir administered early in critical illness will effectively suppress CMV reactivation in CMV seropositive adults with sepsis-associated acute respiratory failure, thereby reducing lung damage and accelerating recovery from respiratory failure by direct and indirect mechanisms, and leading to improved clinical outcomes.

Study Design: Multicenter randomized placebo-controlled double-blind trial, [randomized in blocks for balance across study sites, with interim analyses of safety].

Study Duration: 180 days per patient

Study Product: Ganciclovir sodium: 2-amino-9-76,9-dihydro-3H-purin-6-one.
 Placebo for ganciclovir: [normal saline].

Study Regimen: 500 adults will be randomized in a 1:1 ratio to receive either the study drug or placebo. Participants randomized to intervention will use IV ganciclovir only. Participants will receive ganciclovir or normal saline twice daily from day 1 through day 5 and once a day from day 6 through day 28, hospital discharge, death, whichever occurs earlier.

		Schedule of administration*	
		Day 1 through Day 5	Day 6 through Day 28 or hospital discharge, whichever occurs earlier
Arm	N	Twice daily	Once daily
1	250	Ganciclovir 5 mg/kg intravenously	Ganciclovir 5 mg/kg intravenously
2	250	Normal saline intravenously	Normal saline intravenously
Total	500		

* "Day" on this table refers to study day. Day 1 is the first day of study drug administration.

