2.5 Sample Size and Power

To estimate the required sample size for this study, we used ventilator-free days (VFD) data from the GRAIL Phase 2 trial and available literature on RSFDs, assuming similar variance. A clinically meaningful difference in RSFDs between treatment arms was assumed to be 2.74 days, with an empirically estimated standard deviation of 9.4 days. To detect this difference with 85% power using a two-sided test at a 5% significance level, a total sample size of 426 participants (213 per group) was required for the primary analysis.

To account for feasibility and potential dropout—including 1% lost to follow-up and 2% early discontinuation due to negative CMV ELISA results—the final sample size was increased to 500 participants. A pre-specified sample size re-estimation was conducted after 50% of participants had reached the primary endpoint; based on the observed data, the original sample size was retained.

Mortality was included as a secondary endpoint. Assuming a 20% mortality rate in the control arm, the final sample size of 500 provides 80% power to detect a hazard ratio of 0.52 between the Ganciclovir and placebo groups.

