We do not expect this intervention to lead to a statistically significant difference in mortality between treatment groups. Nonetheless, mortality is a common and expected endpoint in critical care clinical trials, and it is a component of our primary outcome RSFDs. As such, we will include mortality as a secondary endpoint in this RCT. The risk of death is typically high (approximately 20%) in the patient population included in our trial. Table 6.3 shows the largest relative risk (for mortality) that we can detect in the treatment versus control group, with a sample size of 500 (including dropouts) and 80% power, and for different assumptions of overall mortality in the control arm (ranging from 10-35%).

Table 6-3. Detectable Relative Risk (Hazard Ratios) under different scenarios of control arm mortality with a two-sided test, 80% power and type I error rate of 5%.

Secondary outcome	Control arm assumption (%)	Hazard Ratio detectable*
Mortality (at 28 days)	35	0.62
	30	0.60
	25	0.56
	20	0.52
	15 [‡]	0.45
	10	0.35

* Assumes control arm mortality rate in table, power = 80%, and 0.05 alpha

‡ From GRAIL Phase 2

Based on this table, with the current sample size of 500 and assuming a control arm mortality of 20% (more realistic assumption of mortality for GRAIL Phase 3), the proposed trial will have 80% power to detect a hazard ratio of 0.52 for mortality between the Ganciclovir arm and the Placebo arm.

6.2 Statistical Analyses for Endpoints.

6.2.1 Primary Endpoint.

We will first compare baseline characteristics of the ganciclovir and placebo groups in assessment of the randomization process. Then to test the primary hypothesis that the mean difference in RSFDs between groups differs significantly from 0, we will use the 2-sample parametric t-test. The t-test is powerful and will be sufficient for our purpose, even if normality assumption for RSFDs fails to hold, as the t-test is robust to non-normality assumption for $n > 25$. However, as a confirmatory test, we will also use the 2-sample permutation t-test. The permutation test does not require any distributional assumption on the data and is valid under the much weaker assumption of exchangeability (which will be satisfied under controlled settings of a trial). As the next step, we will use the semiparametric efficient and robust method of Davidian

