6.2.2 Secondary endpoints

[figure not shown]
For the quantitative secondary endpoints (including a key secondary endpoint of VFDs or ventilator-free days), the same method as described in the analysis plan for the primary endpoint will be used. For time to event endpoints including CMV reactivation at given thresholds, the Kaplan-Meier method will be used to estimate the probability of not experiencing CMV reactivation by Day 28 for each group. A 95% confidence interval about the group difference in event rates will be computed using the two Kaplan-Meier estimates and the two Greenwood variance estimates. Based on these estimates, a Z-statistic will be used for testing for difference in the group event rates. The multiple testing problem will be handled using a Bonferroni correction, whenever such situations arise. Additionally, multivariate models will be built for the primary endpoint (RSFD) as well as other secondary endpoints, after adjusting for baseline subject characteristics and risk factors for CMV reactivation, using generalized linear models or the semiparametric efficient and robust method of Davidian et al. [89, 90]. The list of baseline characteristics to be considered for adjustment are those listed in (1) under the Exploratory Objectives/Endpoints (Section 5.3). We will repeat the above analyses in several subgroups (separately) as well, including those who are PCR negative at baseline, as well as those that have septic shock, pneumonia, unilateral infiltrates, or lymphopenia at the time of randomization, and by age and sex. In addition, we will repeat the above analyses in the following subgroups as follows: (1) VFDs in those on invasive mechanical ventilation at randomization; (2) RSFDs in those on invasive mechanical ventilation at randomization; (3) RSFDs in those on NIV/high flow at randomization; (4) Intubation after enrollment in those on NIV/HFNC at randomization (i.e. does ganciclovir affect the need for intubation in this subgroup?); (5) RSFDs according to COVID-19 status at randomization; and (6) CMV detection in plasma by day 28 (28 (>0 IU/mL, >1000 IU/mL) in those with invasive mechanical ventilation vs. NIV/high flow at randomization.

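### The SAP provides for Bonferroni across the secondary endpoints without a family or divisor, yet states mortality power at an uncorrected 5%: 80% holds only if mortality is outside the family, and falls to about 51–54% if it is inside

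*SAP*

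**What the plan says.** **Multiplicity.** SAP 5, under secondary endpoints: "Where applicable, Bonferroni correction will be used to adjust for multiple comparisons across secondary endpoints". Protocol 6.2.2: "The multiple testing problem will be handled using a Bonferroni correction, whenever such situations arise". Neither document lists the endpoints in the family, gives the divisor, or says whether mortality is in it.

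**Mortality as a secondary endpoint.** SAP 2.5: "Mortality was included as a secondary endpoint". It is item 3 of the nine secondary outcomes in SAP 2.2 and protocol 5.2.1.

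**Mortality power.** SAP 2.5 claims 80% power at HR 0.52. Its premise is "Assuming a 20% mortality rate in the control arm". The figure comes from protocol 6.1.2, Table 6-3. The caption of that table reads "with a two-sided test, 80% power and type I error rate of 5" per cent, and its footnote repeats "power = 80%, and 0.05 alpha". The text before the table ties the calculation to the full trial: "with a sample size of 500 (including dropouts) and 80% power".

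**Mortality as a safety endpoint.** SAP 9 compares deaths by log-rank test and a Cox HR with a 95% confidence interval, and mentions no multiplicity adjustment. SAP 10 item 3 says that the secondary mortality analysis follows SAP 9. Protocol 6.5.1.1 gives death its own one-sided 0.025 error rate in each direction. Its illustrative O'Brien-Fleming table puts the harm boundary at HR 1.480 (Z = 1.96) when 100 deaths have occurred.

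**The concern.** The same mortality comparison appears in three places with no single error rate. The power statement uses 0.05. The safety monitoring plan uses 0.025 per side. The multiplicity sentence, read literally, covers every secondary endpoint and would test mortality at 0.05 divided by some unstated number.

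Two things are at stake. First, the stated 80% power holds on only one reading of SAP 5, and the SAP does not say which reading applies. Second, the SAP reports that NHLBI closed enrollment over safety and futility concerns, so the direction of the mortality effect is a sensitive question. Under a corrected alpha, an observed excess of deaths could cross the protocol's own boundary and still be called non-significant as a secondary endpoint. With the family undefined, that choice could be made after the results are known.

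**Working it through.** **Inputs.** 500 randomized 1:1, so 250 per arm (SAP 2.1); control mortality 20% (SAP 2.5, Table 6-3); HR 0.52; two-sided alpha 0.05 (Table 6-3); 100 expected deaths (protocol 6.5.1.1).

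**Step 1. Reproduce the plan's 80%.** Under proportional hazards, treated-arm mortality is 1 − 0.80^0.52 = 0.110. Expected deaths are 250 × (0.20 + 0.110), about 77.4. Power at two-sided 0.05:

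- Two proportions (0.20 v 0.110, 250 per arm): 80.0%.
- Schoenfeld: Φ(√77.4 × |ln 0.52| / 2 − 1.960) = 82.0%.
- Freedman: Φ(√77.4 × 0.48 / 1.52 − 1.960) = 79.3%.

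The stated figure is right for its stated alpha.

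**Step 2. Choose the divisor k.** The plan gives none, so k is an assumption. Nine outcomes are listed. In SAP 10, two of them have no formal test: oxygenation is shown as boxplots, and Grade 3 or higher adverse events are given as a listing. That leaves k = 7. SAP 5's general rule for quantitative secondary endpoints could bring oxygenation back (k = 8). Counting day 28 and day 180 mortality separately, and two CMV thresholds in each of two specimen types, would give 7 + 1 + 3 = 11.

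**Step 3. Power if mortality is in the family.** Start from exactly 80% at 0.05 and change only the critical value: power = Φ(1.960 + 0.842 − z), where z is the two-sided critical value at 0.05/k.

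| k | alpha | power at HR 0.52 |
|---|---|---|
| 1 (mortality outside the family) | 0.0500 | 80% |
| 2 | 0.0250 | 71% |
| 7 | 0.0071 | 54% |
| 8 | 0.0063 | 53% |
| 9 | 0.0056 | 51% |
| 11 | 0.0045 | 49% |

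For k = 7, z = 2.690 and Φ(0.112) = 0.544. For k = 9, z = 2.773 and Φ(0.029) = 0.511. The three formulas of step 1, evaluated directly, give 53.5–57.4% at k = 7 and 50.2–54.1% at k = 9.

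**Step 4. Smallest harmful HR that reaches significance.** HR = exp(2z/√D), with D deaths and equal arms.

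| alpha | D = 100 | D = 77 |
|---|---|---|
| 0.05 | 1.48 | 1.56 |
| 0.05/7 | 1.71 | 1.85 |
| 0.05/9 | 1.74 | 1.88 |

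The 1.48 at 100 deaths equals the 1.480 in the protocol's table. With a corrected alpha, an observed HR of 1.6 at 100 deaths would lie beyond that boundary and yet be non-significant as a secondary endpoint.

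**The case against.** A reader might infer that the SAP corrects mortality and that its true power is therefore 51%. The documents do not support this. Both multiplicity sentences are conditional, and neither names mortality. SAP 9 places deaths under safety with no adjustment, SAP 10 item 3 follows SAP 9, and protocol 6.5.1.1 gives death its own error rate. An unadjusted test is the more natural intention, and on that reading nothing in the plan contradicts itself. The 51% also depends on counting two outcomes that have no planned test in SAP 10.

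The protocol further says that it does not expect a significant mortality difference (6.1.2) and that the study was not specifically powered for the secondary endpoints (4.5.2). The 80% is thus an illustration of what could be detected. The Cox HR and its 95% interval will be reported whatever is decided about Bonferroni, so a harm estimate would not be hidden.

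All of this stands, and it limits the point to an unresolved ambiguity with conditional consequences. It does not remove the point. The reading that excludes mortality is written nowhere, the SAP's phrase refers to the secondary endpoints as a group, and every reading that includes mortality costs power, even k = 2.

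**Conclusion.** The gap is real: the Bonferroni family and divisor are undefined, and the mortality power statement holds only if mortality lies outside that family. If it lies inside, planned power at HR 0.52 is about 54% (k = 7) or 51% (k = 9), and the harm threshold at 100 deaths is about 1.71–1.74, against the protocol's 1.480. These figures assume an equal alpha split, 250 per arm, 20% control mortality and proportional hazards.

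The 80% is not an error at its own alpha, and the documents do not establish that mortality will be corrected. Because enrollment closed early, the figures describe the planned design and not the power or threshold of the final analysis. The ambiguity about which alpha applies remains in the final analysis all the same.

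**What to change.** In SAP 5:

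1. State that mortality is outside the multiplicity family and is tested two-sided at 0.05, consistent with SAP 9 and protocol 6.5.1.1. If the sponsor prefers to keep it inside, name the family and divisor, and restate the 80% in SAP 2.5 and Table 6-3 at the corrected alpha.
2. Name the efficacy secondaries that have a formal test, and apply Holm's step-down procedure to them in place of Bonferroni. Holm controls the same familywise error and never rejects fewer hypotheses.

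Both are wording changes and need no new data. The cost of the first is that the familywise error statement then does not cover mortality, which the report should say. The choice should be on record before the final mortality comparison is seen.

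Two further changes may seem natural but are not recommended. Testing ventilator-free days only after the primary endpoint succeeds is a trade-off, since it bars any such claim if the primary endpoint fails. Taking adverse events out of the family would change nothing, because no test of them is planned.
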